# 1. AMENDMENT HISTORY

Amendment No.	Protocol Version No.	Date issued	Author(s) of changes	Details of Changes made	

# 2. SYNOPSIS

Study Title	Real time computer aided detection and characterisation of colorectal polyps; a prospective multi-centre randomised controlled superiority trial (ColoVision)
Internal ref. no.	PHU/2022/09
Problem statement	Colorectal cancer is a major health problem. Most colorectal cancers develop from precursor lesions (polyps), and early detection and removal of these polyps can reduce rate and improve outcome of colorectal cancer.
	Colonoscopy is the gold standard test to detect and remove polyps, however there is still significant polyp miss rate. Moreover, the concept of optical diagnosis of polyps has been recommended by various guidelines, however its implementation outside expert and academic centres is still limited.
	Computer aided detection (CADe) and computer aided diagnosis (CADx) of polyps is rapidly progressing and recent studies have shown promising results. However, there is still lack of high-quality data from well-designed and implemented randomised trials and hence the need for this study.
Research question / hypothesis	Our hypothesis is that the CAD device used in this study (WISE VISION®) can significantly improve endoscopists' adenoma detection rate (ADR) as well as their real time optical diagnosis to reach PIVI threshold of 90% NPV, compared to endoscopists not using the CAD device.
Study Design	This is an investigator initiated and led multi-centre randomised control superiority trial. The study will be using the NEC WISE VISION® device which has two functions: CADe and CADx and we will assess the impact of both.
	Participants will be randomised into two groups. The control group will have a standard colonoscopy (without CAD device support), and the intervention group will have colonoscopy with CAD device (both CADe and CADx)
	All patients (both in control and intervention group) will receive standard care. All decisions taken during the colonoscopy procedure will be taken by the endoscopists as per standard protocols.
Study Participants	Patients undergoing a colonoscopy

Planned Sample Size	CADe: 654 participants				
	CADx: 200 diminutive rectosigmoid polyps (588 total polyps)				
Follow-up duration	28 days (+/- 14 days)				
Planned Study Period	12 months				
Primary Objective	
 
To evaluate the impact of the CAD system on endoscopists' detection of colorectal polyps
 
				
	
 
To evaluate the impact of the CAD system on real time characterisation (optical diagnosis) of polyps compared to histology.
 
				
Secondary Objectives	To evaluate the effect of the CAD device on other polyp detection parameters.				
Primary Endpoints	Adenoma detection rate in both groups PIVI-2: NPV of adenoma diagnosis in diminutive (<5mm) rectosigmoid polyps in both groups				
Secondary Endpoints	Polyp detection rate (PDR) in both groups Adenoma per colon (APC) in both groups PIVI-1: agreement between surveillance interval decisions based on histology and that based on the combination of histology of non- diminutive polyps and optical diagnosis in both arms Diagnostic performance measures in both groups (sensitivity, specificity, accuracy, NPV, PPV, AUC) according to various factors (eg endoscopist's experience) Withdrawal time in both groups				
Intervention (s)	Colonoscopy plus WISE VISION® CAD device				

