## 7.1 Primary Objective

- To evaluate the impact of the CAD system on endoscopists' detection of colorectal polyps
- To evaluate the impact of CAD characterisation system on endoscopists performance in optical diagnosis of diminutive colorectal polyps compared to histology

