## 8.1 Summary of Study Design

This will be a multi-centre randomised control superiority trial. Participants will be randomised to either standard colonoscopy (control arm) or colonoscopy plus WISE VISION® CAD device (intervention arm). The CAD device has both detection and characterisation functions and there are 2 elements within the study. Firstly the study will aim to assess the impact of computer aided detection and secondly computer aided characterisation.

When polyps are identified, these will be recorded and the endoscopist will be required to assess this and indicate their optical diagnosis accordingly. For patients randomised to colonoscopy plus CAD, the CADx will then be carried out and the results recorded. Polyps will be treated according to standard care.

Polyps detected by the endoscopists but missed by the CADe device will also be recorded. The total number of polyps identified and the endoscopist diagnosis will be recorded for both arms. The histology results of the polyps removed will be collected.

Figure 1: Study Procedure Flowchart

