## 8.2 Primary and Secondary Endpoints/Outcome Measures

## **Primary End points**

Adenoma detection rate in both arms PIVI-2: NPV of adenoma diagnosis in diminutive (<5mm) recto-sigmoid polyps in both arms

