## 10. SAMPLING

- This is powered as a superiority trial.
- For computer aided detection, the ADR of competent but non-expert endoscopists is assumed to be 20% and we believe that CADe will increase it to 30% (expert level). In order to demonstrate a difference of 10% between the two groups with an 80% power and a significance level (alpha) 0.05; we will need 588 patients (294 per group). We will over recruit by 10% (max total of 654) to allow for drop outs, poor bowel prep, incomplete dataset etc. Interim analysis will be done after 50% recruitment
- For computer aided diagnosis, the NPV of endoscopists is assumed to be 75%, and we believe the NPV of endoscopist plus CADx will be 90%. To achieve this with an 80% power and significance level (alpha) of 0.05, we will need to assess 200 diminutive recto-sigmoid (100 per group) polyps (588 total polyps), in an estimated 168 patients. We will plan to over recruit by 10% to allow for incomplete data (220 diminutive recto-sigmoid polyps, 647 total polyps). Interim analysis will be done after 50% recruitment

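### The between-arm NPV measures the whole device (CADe plus CADx), but the Protocol credits it to CADx, and CADe can move it by changing which polyps are read

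*Protocol*

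**What the plan says.** The Protocol has two arms. In the synopsis, "The control group will have a standard colonoscopy (without CAD device support"), while "the intervention group will have colonoscopy with CAD device (both CADe and CADx"). No arm has only one of the two functions. Patients are randomised 1:1 (Randomisation, 11.3); polyps are not.

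The second primary endpoint in 8.2 is "NPV of adenoma diagnosis in diminutive (<5mm) recto-sigmoid polyps in both arms". Three places attach this comparison to the characterisation function:

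- 7.1 gives the objective as "To evaluate the impact of CAD characterisation system on endoscopists performance in optical diagnosis of diminutive colorectal polyps compared to histology".
- 8.1 presents two separate elements: "Firstly the study will aim to assess the impact of computer aided detection and secondly computer aided characterisation".
- Section 10 sets the planning values: "the NPV of endoscopists is assumed to be 75%, and we believe the NPV of endoscopist plus CADx will be 90"%.

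Section 10 also assumes that CADe raises the ADR from 20% to 30%. Among the secondary endpoints, 8.2 lists sensitivity and specificity per arm, without restricting them to diminutive rectosigmoid polyps. For characterisation, 14.2 plans a descriptive percentage of polyps correctly identified against histology.

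**The concern.** NPV is not a property of the reader alone. It also depends on how many of the polyps being read are adenomas. If the arms differed only by CADx, a gain in NPV would be a gain from CADx. Here they also differ by CADe, and the first primary hypothesis is that CADe changes what is found. The two NPVs therefore come from sets of polyps that the Protocol itself expects to differ.

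If CADe mainly adds small non-adenomatous rectosigmoid polyps, NPV rises with no change in reading accuracy. If it mainly adds adenomas, NPV falls and can hide a real benefit of CADx. At stake is the sentence the trial may write about its second primary objective: a difference, or the lack of one, could be credited to the wrong function of the device.

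**Working it through.** **1. The plan's own figure.** Section 10 asks for "200 diminutive recto-sigmoid (100 per group) polyps (588 total polyps"), with the condition "To achieve this with an 80% power and significance level (alpha) of 0.05". For two independent proportions, two-sided, with pooled variance under the null:

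n per group = [1.96·√(2·0.825·0.175) + 0.8416·√(0.75·0.25 + 0.90·0.10)]² / 0.15² = (1.0532 + 0.4433)² / 0.0225 = 99.5, so 100 per group and 200 in total.

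The figure reproduces. The calculation makes no allowance for a difference in polyp mix between the arms.

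**2. How NPV depends on the mix.** With adenoma share p,

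NPV = sp(1−p) / [sp(1−p) + (1−se)p].

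In odds form, NPV/(1−NPV) = [sp/(1−se)] × (non-adenomas/adenomas). The Protocol gives no sensitivity, specificity or adenoma share. Assume se = sp = 0.75 in both arms (no CADx effect) and 50 adenomas per 100 polyps in the control arm. The odds are then 3 × (non-adenomas/adenomas), and the control NPV equals the planned 75%.

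| Added by CADe per 100 polyps | Adenomas / non-adenomas | Adenoma share | NPV odds | NPV |
|---|---|---|---|---|
| nothing | 50 / 50 | 50.0% | 3.00 | 75.0% |
| 25 non-adenomas | 50 / 75 | 40.0% | 4.50 | 81.8% |
| 25 non-adenomas, 10 adenomas | 60 / 75 | 44.4% | 3.75 | 78.9% |
| 15 of each (proportionate) | 65 / 65 | 50.0% | 3.00 | 75.0% |
| 20 adenomas | 70 / 50 | 58.3% | 2.14 | 68.2% |

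**3. A rough bound from the Protocol.** Section 5 says that up to 23% of polyps are missed. If that applied to this subset, CADe could add at most 23/77 = 29.9 polyps per 100 found.

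- All non-adenomas: odds 3 × 79.9/50 = 4.79, NPV about 83%.
- All adenomas: odds 3 × 50/79.9 = 1.88, NPV about 65%.

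**4. Effect on the planned test.** This uses a second set of assumptions: specificity 0.80, control adenoma share between 0.30 and 0.50, sensitivity chosen so that control NPV is 0.75, and the plan's count of 100 per group.

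| Shift in adenoma share | No CADx effect: CAD-arm NPV, chance of a significant result favouring CAD | True CADx effect (NPV 0.90 at the control mix): CAD-arm NPV, power |
|---|---|---|
| none | 0.75, 2.5% | 0.90, 80% |
| 5 points down | about 0.79, 9–11% | – |
| 10 points down | 0.82–0.84, 21–33% | – |
| 5 points up | – | about 0.88, 64–66% |
| 10 points up | – | 0.85–0.86, 44–48% |

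A shift of 10 points is close to the extreme in step 3, where the share runs from 50/129.9 = 38.5% to 79.9/129.9 = 61.5%.

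**5. Precision of a standardised NPV.** Take the assumptions of step 2 with 100 polyps per arm. Half are read as non-adenoma, so the crude NPV rests on 50 polyps per arm. The SD of the difference is √(2·0.75·0.25/50) = 0.087. With NPV standardised to a common prevalence (delta method), the variance of the log-odds per arm is 0.25/(50·0.75) + 0.75/(50·0.25) = 0.0067 + 0.0600 = 0.0667. The SD of the difference is 0.75·0.25·√0.0667·√2, or about 0.07. In this case standardising does not widen the interval.

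**The case against.** The strongest reply is that the hypothesis in the synopsis concerns the device as used, against endoscopists without it, and the synopsis objective speaks of the CAD system. For that question patients are randomised, the contrast is valid, and any change in polyp mix is part of the device's effect. Using both functions in one arm is a stated choice. This stands. A reader might infer that the second primary comparison is invalid or unanswerable; the documents do not support that. Only attribution to CADx is affected.

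Second, 8.2 already plans sensitivity and specificity per arm. If accuracy were equal and only the mix moved, those measures would tend to show it. So it would be wrong to say that the plan has nothing that could reveal the artefact. What remains is that they are secondary, not stated for this subset, and not tied to the claim about CADx.

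Third, a reader might infer that a change in mix alone could produce the whole planned gain. Under the assumptions of step 2, NPV reaches 90% only at an adenoma share of 25%. CADe would then have to add 100 non-adenomas and no adenomas per 100 polyps, far beyond the 29.9 in step 3. The Protocol gives neither the direction nor the size of any shift.

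Last, such supporting analyses often sit in a statistical analysis plan, which was not available here. That is fair for the analyses. The wording of the objective, and whether a diagnosis after CADx is captured during the procedure, are Protocol matters.

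**Conclusion.** The point holds as one of attribution. The between-arm NPV validly estimates the effect of CADe plus CADx together; 7.1, 8.1 and 10 go further and assign it to CADx. In the illustrative cases the mix alone moves NPV by between −6.8 and +6.8 points, against a planned gain of 15. A mixed addition moves it by 3.9 points and a proportionate one by none. If the miss rate quoted in section 5 applied here, the extremes would be about 65% and 83%. All these figures rest on assumed accuracy and adenoma share, and on accuracy being the same for the extra polyps. Polyps found only with CADe may also be easier or harder to read, which would add to or offset the shift. The sample size of 200 is arithmetically correct and is not in question.

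**What to change.** In 8.2 and 14.2:

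1. Keep the between-arm NPV as the co-primary endpoint and describe it as the effect of the whole device. Align the wording of 7.1, 8.1 and 10 with this.
2. For diminutive rectosigmoid polyps, report as supporting analyses the adenoma share, sensitivity and specificity in each arm, and the NPV standardised to the adenoma share pooled over both arms.
3. Base any statement that CADx itself improves optical diagnosis on a same-polyp comparison in the CAD arm: the endoscopist's diagnosis before CADx against the diagnosis after it, both judged against histology.
4. Make the diagnosis after CADx an explicit CRF field, unless the item in 11.4 on the outcome of the endoscopist's assessment already holds it. Section 8.1 already has the endoscopist's diagnosis recorded before CADx is run.

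Histology, optical diagnosis, size and site are already collected, so the cost is analysis wording and at most one CRF field. The field should be settled before recruitment, because a reading not recorded during the procedure cannot be recovered. Standardising removes differences in prevalence but not in polyp difficulty, which is why the paired comparison is needed as well.

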# 3. ABBREVIATIONS

ADR	Adenoma detection rate
AI	Artificial intelligence
AMR	Adenoma miss rate
APC	Adenomatous polyposis coli
BCSP	Bowel cancer screening programme
BLI	Blue Light Imaging
CADe	Computer aided detection
CADx	Computer aided diagnosis
CNN	Convolutional neural networks
CRF	Case report form
FAP	Familial adenomatous polyposis
GCP	Good clinical practice
HDWL	High definition white light
IBD	Inflammatory bowel disease
ITT	Intention to treat
КРІ	Key performance indicators
MSI	Microsatellite instability
NBI	Narrow band imaging
PDR	Polyp detection rate
PIS	Patient information sheet
PIVI	Preservation and Incorporation of Valuable endoscopic Innovations
RCT	Randomised controlled trial
L	

## 4. LAY SUMMARY

Bowel cancer is now the fourth most common form of cancer in the UK according to cancer research UK. We know that some small growths in the lining of the bowel called polyps can turn into cancers if left long enough and that early detection and removal of these polyps can prevent cancers developing.

Colonoscopy is the gold standard test to identify, diagnose and remove these polyps but we also know from research that polyps can be missed at colonoscopy. Artificial intelligence in health care is becoming increasingly common, and technology to improve detection of polyps has been developed, known as Computer Aided Detection CADe and Diagnosis (CADx). Early studies have shown promising results that CAD increases the detection of polyps and is able to recognise whether or not they are the type of polyps which have the potential to turn into cancers, however high-quality data from well designed randomised trials is still limited and hence the need for this study

Several devices for computer aided detection of polyps have been produced and are currently in use in endoscopy units around the world. In this study, we aim to examine how an approved device (WISE VISION®) can support endoscopists on detection and assessment of colorectal polyps.

## 5. BACKGROUND AND RATIONALE

## **Colorectal neoplasia and cancers**

It is well recognised that colorectal cancer develops through the accumulation of series of mutations in a stepwise order. Different pathways have been identified in the pathogenic process. One of the first to be described was the adenoma-carcinoma sequence(1), or what is also known as the "traditional" pathway. The adenomatous polyposis coli (APC) tumour suppressor gene has been identified as one of the early mutations(2) occurring in the sequence. Germline mutations in the APC gene have been associated with familial cancer syndromes such as familial adenomatous polyposis (FAP) and Lynch syndrome, however most colorectal cancer are due to sporadic mutations. Further mutations in numerous genes including K-ras, p53 and 18q loss have also been identified. These occur in two main pathways- the chromosomal instability (CIN) or microsatellite instability (MSI) pathways(3) with the former accounting for approximately 85% of sporadic colorectal cancers(4).

More recently, the "serrated" pathway has been described in colorectal carcinogenesis. Serrated polyps form a heterogenous group of intestinal polyps including sessile serrated lesions as well as hyperplastic polyps which do not harbour malignant potential. This pathway only accounts for a small portion of colorectal cancers(3). Tumours which develop via the serrated pathway display early mutations in the BRAF(5) or K-ras oncogenes, distinct from the adenoma-carcinoma pathway. It is believed that the serrated pathway leads to accelerated cancer growths and are often the cause of interval cancers- those developing in shorter periods of time between surveillance. Sessile serrated lesions tend to be small, proximal lesions and can be easily missed without meticulous examination of the bowel.

## Detection and characterisation of colorectal neoplasia

Our knowledge of the formation of colorectal cancers has led to the introduction of screening such as the Bowel Cancer Screening Programme (BCSP) in the UK. In addition, the need for surveillance has been recognised. Colonoscopy is the 'gold standard' test for assessment of the colon and rectum. Various key performance indicators (KPI) are in place to maintain standards in colonoscopy. This includes adenoma detection rate (ADR) where endoscopists should be aiming for 20%(6), although polyp detection rate (PDR) is often used as a surrogate marker. However, evidence shows that up to 23%(7,8) of polyps are missed on colonoscopy despite one study suggesting that for each 1% rise in ADR, there was a 3% reduction in the risk of cancer(9).

Once identified, polyp characterisation is essential to correctly manage them. There is now an array of enhanced imaging modalities available on modern colonoscopes to assist with differentiating lesions, such as blue light imaging (BLI), narrow band imaging (NBI) as well as standard high definition white light (HDWL) imaging. Estimating the size of polyps endoscopically can be challenging. We know the risk of a diminutive (<5mm) polyp harbouring a cancer is very low(10)(11) and there has been interest in "resect and discard" or "diagnose and leave" in these polyps(12,13). Similarly, the literature suggests polyps over 20mm are more likely to harbour a cancer with the risk being estimated between 2-6%(14). Knowing this, being able to estimate lesion size endoscopically has also drawn interest with the advances in CADx.

## Computer aided detection and diagnosis and its use in the colon and rectum

Computer aided detection devices utilises artificial intelligence (AI) algorithms to perform various tasks. It is becoming increasingly utilised in medicine and has gained particular interest in the field of endoscopy due to the image-based nature of it and the use of pattern recognition. This uses a specific element of AI called Convolutional Neural Network (CNN)(15), involving complex matrix computations to predict the likelihood of what an image shows. Several CAD devices have already been validated (14) for in-vivo polyp detection.

Several recent studies have demonstrated promising performance of CAD devices in polyp detection and characterisation (15). However, most of these studies were performed on endoscopic images and videos, and the number of real time and randomised studies is still very limited. Only 5 randomised trials studying CAD polyp detection have been published and these are mostly done in the far East. Therefore, there is a significant need for Western and UK based randomised trials to study this important area of endoscopy research, and hence this study.

The CAD device in this study (WISE VISION® NEC Japan) is an approved device (CE marked) and already in use in different endoscopy departments around the world(17). This device is fully compatible with all major endoscopy processors. It has two main functions, detection of polyps (CADe) and characterisation of polyps (CADx). The characterisation function classifies polyps according to their likely precited histological diagnosis (neoplastic vs non-neoplastic). The device showed very promising results when evaluated on endoscopic images and videos(18) (ex-vivo), however it has not been assessed in a randomised trial in real time, hence this study.

# 6. PRELIMINARY STUDIES AND EXPERIENCE OF INVESTIGATORS

The Chief Investigator of this study is experienced in running endoscopy clinical trials including studies on the application of AI in endoscopy. All co-investigators and members of the research team are GCP certified and have experience in running various endoscopy-based studies.

## 7. AIMS AND OBJECTIVES

The aim of this study is to assess whether CAD (NEC WISE VISION®) improves polyp detection and characterisation.

## 7.1 Primary Objective

- To evaluate the impact of the CAD system on endoscopists' detection of colorectal polyps
- To evaluate the impact of CAD characterisation system on endoscopists performance in optical diagnosis of diminutive colorectal polyps compared to histology

# 7.2 Secondary Objectives

- To assess the diagnostic performance of the CAD system on detection of colorectal polyps according to their size, location and morphology
- To evaluate the diagnostic performance of the CAD system on characterization of colorectal polyps based on size, location and morphology
- Evaluate the false positives and false negatives by the CADe system to understand predictors of wrong CADe detection
- Evaluate the cost implications of the CAD system
- Evaluate the impact of the CADe system on complications from colonoscopy and polyp removal

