## 11.4 Study Assessments

Baseline characteristics will be recorded for all participants. Basic demographics will be recorded to include:

- Age
- Sex
- Co-morbidities and ASA score
- History of previous polyps/bowel conditions

During the colonoscopy the following will be recorded in all patients:

- Endoscopist including level of experience (number of life time procedures)
- Indication
- Bowel preparation used and quality
- Use of sedation/general anaesthetic
- Procedure start and finish time and time of maximal intubation
- Comfort score
- Adverse events
- Polyps detected to include the endoscopists optical diagnosis and assessment of size, morphology using the Paris classification, site and details of their removal.
- Still image/video of polyp (where available)

For patients randomised to colonoscopy plus CAD the following additional data will be recorded:

- Total number of potential polyps identified by CADe
- CADx diagnosis of polyps identified
- Outcome of assessment by endoscopist e.g. confirmed as polyp, characterisation assessment

Post colonoscopy:

- Adverse events will be recorded
- Histology of any polyps removed will be recorded to correlate with the endoscopist/CADx assessment of the lesion.

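### The single-pass design cannot identify CADe's false-negative rate; it gives only the share of endoscopist-confirmed polyps that CADe did not flag

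*Protocol*

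**What the plan says.** Two secondary objectives in Protocol section 7.2 concern the detection function of the device itself. One is "To assess the diagnostic performance of the CAD system on detection of colorectal polyps according to their size, location and morphology". The other is "Evaluate the false positives and false negatives by the CADe system to understand predictors of wrong CADe detection".

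The design and data collection behind them are as follows.

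- Section 8.1 describes parallel arms with one procedure per patient: "Participants will be randomised to either standard colonoscopy (control arm) or colonoscopy plus WISE VISION" CAD.
- Section 8.1 gives the only stated source of CADe misses: "Polyps detected by the endoscopists but missed by the CADe device will also be recorded".
- Section 11.4 lists, for the CAD arm, "Total number of potential polyps identified by CADe" and "Outcome of assessment by endoscopist e.g. confirmed as polyp, characterisation assessment". The prompts are therefore judged by the endoscopist performing the examination.
- Section 11.4 keeps images of polyps only where they exist. Section 8.1 collects histology for removed polyps. Section 11.6 requires no extra follow-up.

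The background (section 5) states that "evidence shows that up to 23%(7,8) of polyps are missed on colonoscopy". It also describes sessile serrated lesions as typically small, proximal and easy to overlook.

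**The concern.** A false-negative rate needs a count of the polyps that were there to be found. The text describes no tandem examination, no independent reading of full withdrawal video and no follow-up examination. The reference set is whatever the endoscopist confirmed during a single pass with the device running. A polyp that neither noticed drops out of both numerator and denominator. The endoscopist also sees the prompts, so the comparator is not independent of the device.

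If the observable share is published as device sensitivity or as a false-negative rate, readers may take it as better than the device deserves. Size, location and morphology are also the features that make a polyp easy to miss. The loss from the denominator may therefore differ between the subgroups being compared and mute the predictors that the objective is meant to find.

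**Working it through.** The protocol gives no figure for CADe sensitivity, so there is none to reproduce. The sample sizes in section 10 are for ADR and NPV and do not bear on this point.

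**Inputs**
- From the protocol: a polyp miss rate at colonoscopy of up to 23% (section 5).
- Assumed: true CADe sensitivity *s*, from 70% to 95%.
- *m*: the chance that the endoscopist also misses a polyp that CADe missed. If misses are independent, *m* equals the endoscopist's miss rate, taken as 23%. Values of 50% and 80% are assumptions that represent overlap.
- *d*: the fraction of true prompts that the endoscopist wrongly dismisses. Assumed.

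**Step 1. Denominator: polyps seen by either, every true prompt confirmed.** The share missed by both is (1 − s)m, so

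apparent sensitivity = s / [1 − (1 − s)m].

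Example: s = 0.80, m = 0.23 gives 0.80 / (1 − 0.20 × 0.23) = 0.80 / 0.954 = 0.839.

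| True s | m = 23% | m = 50% | m = 80% |
|---|---|---|---|
| 70% | 75.2% | 82.4% | 92.1% |
| 80% | 83.9% | 88.9% | 95.2% |
| 90% | 92.1% | 94.7% | 97.8% |
| 95% | 96.1% | 97.4% | 99.0% |

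With m = 23% the excess is 5.2, 3.9, 2.1 and 1.1 points from the top row down. The top right cell implies that 0.30 × 0.80 = 24% of polyps are missed by both. That already exceeds the protocol's 23% for the endoscopist's misses, so it could apply only to a subgroup harder than average.

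**Step 2. Some true prompts dismissed.** These leave the numerator and are counted as false positives:

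apparent sensitivity = s(1 − d) / [s(1 − d) + (1 − s)(1 − m)].

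With s = 0.80 and m = 0.23:
- d = 0: 0.839
- d = 0.10: 0.72 / (0.72 + 0.154) = 0.824
- d = 0.23: 0.616 / (0.616 + 0.154) = 0.800, no bias
- d = 0.30: 0.56 / (0.56 + 0.154) = 0.784, bias reversed

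The apparent value is too high only if m exceeds d.

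**Step 3. Denominator: only polyps the endoscopist found unaided.** Apparent sensitivity is then (0.77 + s − 1 + q) / 0.77, where q is the share missed by both. With s = 0.80:
- independent misses, q = 0.23 × 0.20 = 0.046: 0.616 / 0.77 = 0.80, no bias
- full overlap, q = 0.20: 0.77 / 0.77 = 1.00

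Inflation here needs positively correlated misses. That is plausible, since both work from the same image, but the protocol does not establish it.

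**Step 4. Subgroup contrast.** Assume true sensitivity of 70% in hard-to-see polyps and 95% in easy ones, a gap of 25 points.
- m = 23% in both: 75.2% against 96.1%, a gap of 21 points
- m = 50% in both: 82.4% against 97.4%, a gap of 15 points
- m = 80% (hard) and 23% (easy): 92.1% against 96.1%, a gap of 4 points

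The contrast shrinks in each case. How far depends almost wholly on *m*, which the design cannot estimate.

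**The case against.** The strongest reply is that section 7.2 states objectives, not estimators. The protocol never defines a CADe sensitivity or its denominator. The sensitivity, specificity and AUC endpoints in section 8.2 are for both groups, including the arm without CADe, so they describe optical diagnosis. Section 14.2 fixes no CADe false-negative analysis, and section 8.1 already says in effect that misses are counted among polyps the endoscopist found. ADR, PDR and adenomas per colon are compared between arms in any case. Finally, polyps never brought into view could reasonably be placed outside the task of an image-based detector, and the 23% is an upper figure that does not separate them.

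Much of this stands. A reader might infer that the plan commits the trial to reporting an upwardly biased sensitivity. It does not, because no such estimate is fixed. A reader might also infer that CADe could look equally good in the lesions where it fails most. That rests on the 80% against 23% case in step 4, for which the protocol gives no support; with 23% in both strata most of the gap survives.

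What does not fall away is identification. The objectives ask for the device's detection performance and false negatives, and a later analysis plan can choose a denominator but cannot supply polyps that were never recorded. Missed pathology appears in section 12.2 among the complications to be noted in the CRF, but without a second look it is not a systematic reference. Restricting the measure to polyps that came into view would narrow the problem, but the protocol does not make that restriction, and polyps in view yet unnoticed by both would still be lost.

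**Conclusion.** The point holds as a limit on what these two objectives can deliver. The data support the proportion of endoscopist-confirmed polyps that CADe did not flag, conditional on the polyp being seen. That is not the device's false-negative rate.

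The likely direction is understatement of that rate, greater for hard-to-see lesions, if CADe and endoscopist tend to miss the same polyps. The direction is not certain, because wrongly dismissed true prompts work against it and can cancel or reverse it. Nor can the size be determined. Apparent sensitivity is about 1 to 5 points too high under independent misses at 23%, an assumed true sensitivity of 95% down to 70%, and no dismissed prompts. It is further off if misses overlap.

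Severity is minor. Only secondary objectives are touched. The randomised ADR comparison does not use a CADe false-negative count, and it would be wrong to read this point as casting doubt on it.

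**What to change.** 1. In section 7.2, answer the detection objective by a randomised comparison, CAD arm against control arm, of adenomas and of polyps per colonoscopy by size, location and morphology. Section 11.4 already records size, Paris morphology, site and histology of removed polyps in both arms. This measures the effect of endoscopist plus CAD, including polyps that would otherwise have gone unseen, and needs no reference standard for missed polyps.
2. Restate the false-negative objective as the proportion of endoscopist-confirmed polyps not flagged by CADe, conditional on being seen. Describe its predictors as predictors of non-flagging among seen polyps, and do not report the result as device sensitivity or a device false-negative rate.

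The cost is rewording two objectives and adding one between-arm table from data already collected, with no extra patients, procedures or readers. The downside is that the sponsor gives up a device-level sensitivity claim for detection, which this design could not support.
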